**Inclusion criteria:**

1. Age  $\geq$  18
2. Cardiologist-confirmed diagnosis of SCAD in the past 3-18 months
3. Internet access (via computer or mobile device)
4. English-speaking and reading

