**Exclusion criteria:**

1. Terminal illness with life expectancy  $<$ 1 year
2. Severe mental illness requiring urgent psychiatric intervention or past-year psychiatric hospitalization
3. Significant cognitive impairment preventing informed consent
4. Deemed unable to complete research procedures
5. Unavailable for intervention sessions (e.g., schedule conflicts)

There are no exclusion criteria with respect to ethnicity or socioeconomic status.

Briefly describe study procedures. Include any local site restrictions, for example, "Subjects enrolled at Mass General Brigham will not participate in the pharmacokinetic portion of the study." Describe study endpoints.

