All study participants will continue to receive standard care. The study procedures differ from standard care in that patients will be approached about the study and invited to participate. Those who are eligible and interested in participating will receive training in an evidence-based skills building program with their peers and a trained instructor. All patients who choose to participate in the study will continue to receive standard care with no other differences in their treatment beyond additional training in psychosocial skills. The alternative is to continue standard care without also participating in the study intervention.

Describe how risks to subjects are minimized, for example, by using procedures which are consistent with sound research design and which do not unnecessarily expose subjects to risk or by using procedures already being performed on the subject for diagnostic or treatment purposes.

To minimize risks, all procedures will be performed in clinically stable participants who meet eligibility criteria. Participant risks are mitigated by excluding participants who are particularly vulnerable including those with severe mental illness, or those who are cognitively impaired, have short life expectancy. Participants will also be told that all participation is voluntary, and they can withdraw from the study at any time. Also, they will be told that the care they receive from their treating providers will in no way be affected by their participation or decision not to participate in this study.

Any serious adverse events (SAEs) will be reported to the IRB. SAEs will be collected and reported from screening to 30 days after the end of the study follow-up period for an individual participant. SAEs will be followed until resolution, stabilization, or until it is determined that study participation is not the cause.

Describe explicitly the methods for ensuring the safety of subjects. Provide objective criteria for removing a subject from the study, for example, objective criteria for worsening disease/lack of improvement and/or unacceptable adverse events. The inclusion of objective drop criteria is especially important in studies designed with placebo control groups.

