
The objective criteria for removal from the study is worsening psychiatric symptoms that become psychiatrically unstable that precludes their participation (e.g., constitute danger to self or others). The PI will let the participants know that if it seems unsafe for them to remain in the study, the PI will contact them. In cases where psychological symptoms are worsening but do not constitute necessary removal from the study, the PI will discuss the concerns with the participant, give them the option to exit the study if they would like, and assist them in connecting to a higher level of care if needed (e.g., by providing mental health referrals).

To ensure the physical safety of participants, we will inform treating cardiologists that physical activity will be tracked as part of the study and obtain approval that it is safe for the participant to

be applying intervention skills to increased physical activity. Following guidelines from a 2018 AHA scientific statement on SCAD, we will advise SCAD patients in the trial to avoid prolonged high-intensity activities, highly competitive or contact sports, activities performed to exhaustion, abrupt increases in physical activity without warm-up, and exercising in extreme temperature.

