### **EQUITABLE SELECTION OF SUBJECTS**

The risks and benefits of the research must be fairly distributed among the populations that stand to benefit from it. No group of persons, for example, men, women, pregnant women, children, and minorities, should be categorically excluded from the research without a good scientific or ethical reason to do so. Please provide the basis for concluding that the study population is representative of the population that stands to potentially benefit from this research.

All adult subjects who satisfy the inclusion/exclusion criteria are eligible for enrollment in this study regardless of sex, race or ethnicity.

When people who do not speak English are excluded from participation in the research, provide the scientific rationale for doing so. Individuals who do not speak English should not be denied participation in research simply because it is inconvenient to translate the consent form in different languages and to have an interpreter present.

Only participants who can read and speak English will be included in the current study, as the intervention and most assessment measures have not been validated for use in non-English speaking populations.

For guidance, refer to the following Mass General Brigham policy:

Obtaining and Documenting Informed Consent of Subjects who do not Speak English

<https://partnershealthcare.sharepoint.com/sites/phrmApply/aieipa/irb/Documents/Obtaining%20and%20Documenting%20Informed%20Consent%20of%20Non-English%20Speaking%20Subjects.pdf>

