Patients who are interested in study participation will be screened for eligibility over the phone by the study RA, who will be CITI certified and trained in all research procedures. The RA will explain the study procedures, answer any questions, and complete an eligibility screening, which will include: confirmation of the patient's age (> 18 years old), SCAD diagnosis in past 3-18 months, internet access, ability to speak and read English, no terminal illness, no severe mental illness or past-year psychiatric hospitalization, no cognitive impairments preventing informed consent, ability to complete research procedures, and availability for planned session times. Confirmation will be based on the patient's verbal report, study staff's clinical judgment, and/or the patient's medical history. The RA will consult with the PI and/or review the patient's electronic medical record to confirm any questions about eligibility. If participants meet study criteria, they will complete the informed consent process described below. The eligibility screener and phone scripts are included in the IRB submission.

Provide details of remuneration, when applicable. Even when subjects may derive medical benefit from participation, it is often the case that extra hospital visits, meals at the hospital,

parking fees or other inconveniences will result in additional out-of-pocket expenses related to study participation. Investigators may wish to consider providing reimbursement for such expenses when funding is available

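### Does the missing rule for patients without cardiologist approval undermine the enrollment and retention outcomes?

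*Combined protocol and SAP*

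**What the plan says.** Two statements in the risk and safety text of Research Design and Methods, placed after the Analysis Plan, bear on who takes part. On minimizing risk: "all procedures will be performed in clinically stable participants who meet eligibility criteria". On physical safety, the team is to "inform treating cardiologists that physical activity will be tracked as part of the study and obtain approval that it is safe for the participant", meaning safe to use what the sessions teach to become more active. The stated ground for taking someone out is mental health alone: "The objective criteria for removal from the study is worsening psychiatric symptoms", once these make continued participation untenable.

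Eligibility elsewhere runs on the listed criteria. The one cardiac inclusion criterion is "Cardiologist-confirmed diagnosis of SCAD in the past 3-18 months", and the nearest exclusion is "Deemed unable to complete research procedures". Equitable Selection of Subjects says "All adult subjects who satisfy the inclusion/exclusion criteria are eligible for enrollment in this study". Recruitment Procedures says of the phone screen: "If participants meet study criteria, they will complete the informed consent process described below". On age, the inclusion list admits patients from 18, while the screen checks "age (> 18 years old), SCAD diagnosis in past 3-18 months".

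Table 1 sets the primary limits: at least 70% of eligible patients enrolling, under 20% ineligible on any one criterion, and no more than 20% attrition. Specific Aim 1 gives a different figure for retention, at least 70%. Research Design and Methods plans about 20 participants in two groups of about 8, allowing for 20% loss.

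**The concern.** On a plain reading, the safety text adds two conditions, clinical stability and a cardiologist's approval, that the criteria and the phone screen do not contain. A patient who meets every listed criterion but is not approved is eligible under Equitable Selection of Subjects and goes on to consent under Recruitment Procedures, yet falls short of the safety text. The removal rule does not cover the case, and the unable-to-complete exclusion does so only loosely, because Aim 2 describes research procedures as surveys, diaries and actigraphy.

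At stake are two primary outcomes with fixed limits. The patient could be called ineligible, eligible but not enrolled, or enrolled and lost. Each choice alters a numerator or a denominator, and nothing settles the choice before the counts are known. With about 20 participants, one patient is worth 1/20 = 5 percentage points. The anticipated loss equals the Table 1 attrition limit, so that line seems to have no room.

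**Working it through.** **Inputs.** From Research Design and Methods: two groups of about 8, 20% anticipated loss, N about 20. From Table 1: enrollment at least 70% of eligible, attrition at most 20%. From Specific Aim 1: retention at least 70%. Assumed, because the documents give no figure: the number of patients without approval, u, taken from 0 to 3; and the number passing the phone screen, S.

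**Planned size.** 2 × 8 = 16, and 16/(1 − 0.20) = 20, which reproduces the plan's figure.

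**Retention, worst case.** Take 20 participants with the full anticipated loss, 0.20 × 20 = 4, and add u further patients counted as enrolled and lost. Attrition is (4 + u)/(20 + u) and retention is 16/(20 + u).

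| u | Attrition | Table 1 (≤20%) | Retention | Aim 1 (≥70%) |
|---|---|---|---|---|
| 0 | 4/20 = 20.0% | met | 16/20 = 80.0% | met |
| 1 | 5/21 = 23.8% | not met | 16/21 = 76.2% | met |
| 2 | 6/22 = 27.3% | not met | 16/22 = 72.7% | met |
| 3 | 7/23 = 30.4% | not met | 16/23 = 69.6% | not met |

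The Table 1 failures come from stacking u on top of a full 20% loss. The plan does not divide that 20% by cause. Three alternatives with u = 1 all meet the limit:
- The patient is one of the 20 and one of the 4 lost: 4/20 = 20.0%.
- The patient is additional, with three other losses: 4/21 = 19.0%.
- The patient is additional, stays in and finishes, with four other losses: 4/21 = 19.0%.

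The last case is open because the approval concerns being more active; the text does not say that a refusal ends participation.

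The class can still matter without stacking. With 20 enrolled, three ordinary losses and two patients stopped for lack of approval, attrition is 5/20 = 25.0% if they count and 3/18 = 16.7% if they are taken out of both numerator and denominator. With only one such patient, the figures are 4/20 = 20.0% and 3/19 = 15.8%, and both pass.

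**Enrollment.** With 20 taking part, the rate is 20/(S − u) if the u patients are ineligible, 20/S if eligible but not enrolled, and (20 + u)/S if enrolled. For u = 1:

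| S | Ineligible | Eligible, not enrolled | Enrolled |
|---|---|---|---|
| 28 | 20/27 = 74.1% | 20/28 = 71.4% | 21/28 = 75.0% |
| 29 | 20/28 = 71.4% | 20/29 = 69.0% | 21/29 = 72.4% |
| 30 | 20/29 = 69.0% | 20/30 = 66.7% | 21/30 = 70.0% |
| 31 | 20/30 = 66.7% | 20/31 = 64.5% | 21/31 = 67.7% |

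The verdict depends on the class only at S = 29 and S = 30. Further from the line it takes more such patients: with five eligible decliners, 20/25 = 80.0% falls below 70% only when four are added to the denominator (20/29 = 69.0%).

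**Clinical stability.** The sentence directly after the stability remark explains the mitigation as leaving out patients with severe mental illness, cognitive impairment or short life expectancy. Those are the first three listed exclusions. Read together, the paragraph summarizes existing criteria rather than adding one. That leaves the approval as the only unplaced condition.

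**The case for a change.** The strongest case for acting is that the approval is a stated physical-safety step, and nothing else in the protocol places it. Clinical judgment at the phone screen is a way of confirming listed items, not an extra criterion. Cardiologist contact at recruitment serves to confirm the SCAD history, and record review may replace it for patients who answer a flyer, so contact before consent is not assured. A class chosen after the counts are seen could favor the result, and a few sentences would prevent that.

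The textual part stands: the timing of the approval and the consequence of a refusal are not written down. The statistical part is weaker. Recruitment is mainly through SCAD clinic cardiologists and cardiologists' patient lists, and a cardiologist is on the study team, so refusals after screening are likely to be few. Table 1 already asks for reasons for ineligibility, reasons for refusal and characteristics of refusers, so a case excluded or declining before enrollment would be visible. The outcomes are descriptive, with no test attached. A reader shown 20/28 and 20/29 with the reason beside them loses nothing.

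The obvious remedy also has a difficulty. Fixing the denominator as everyone who passes the phone screen, while treating a later pre-consent refusal of approval as ineligible, puts the same patient both in and out of it.

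**Conclusion.** No change to the plan follows. What is missing is a detail the team can supply in the ordinary course: obtain the approval, class the rare refusal by the point at which it arose, and report it with its reason. The stability remark most plausibly restates existing exclusions, and the difference between 18 and over and older than 18 is a clerical slip of negligible effect.

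The size is small and conditional. With one refusal, the enrollment verdict depends on class only if 29 or 30 patients pass the screen. Attrition fails the Table 1 limit through one refusal only when that patient is an additional enrolled-and-lost case beyond the full anticipated loss, and retention then still meets the Aim 1 figure. With two or three refusals the sensitivity grows, but nothing in the documents suggests such a number. These conclusions rest on N = 20, the 20% anticipated loss, and an assumed number of refusals that may be zero.

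Whether approval conditions enrollment, and what a refusal entails, is a clinical matter on which no view is taken here. Reconciling the safety text with the criteria and the screen is for the investigators; the analysis of the feasibility outcomes does not depend on it.

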### **FORESEEABLE RISKS AND DISCOMFORTS**

Provide a brief description of any foreseeable risks and discomforts to subjects. Include those related to drugs/devices/procedures being studied and/or administered/performed solely for research purposes. In addition, include psychosocial risks, and risks related to privacy and confidentiality. When applicable, describe risks to a developing fetus or nursing infant.

As in any research study, there is a small risk that confidentiality may be breached; all efforts to minimize this risk will be taken, as outlined above. Patients may face discomfort with intervention procedures, survey questionnaires, and exit interview topics. All measures to maintain participant safety, satisfaction and comfort are detailed above.

### **EXPECTED BENEFITS**

Describe both the expected benefits to individual subjects participating in the research and the importance of the knowledge that may reasonably be expected to result from the study. Provide a brief, realistic summary of potential benefits to subjects, for example, "It is hoped that the treatment will result in a partial reduction in tumor size in at least 25% of the enrolled subjects." Indicate how the results of the study will benefit future patients with the disease/condition being studied and/or society, e.g., through increased knowledge of human physiology or behavior, improved safety, or technological advances.

While participants in this study may not directly benefit from their participation, we anticipate results from this study to benefit future research that seeks to reduce fear and improve health behaviors after SCAD. Participants may benefit from receiving the adapted MBCT intervention in terms of increase in mindfulness skills to cope with health-related fears, opportunity for peer support and clinician attention, and improvement in health behaviors.

### **EQUITABLE SELECTION OF SUBJECTS**

The risks and benefits of the research must be fairly distributed among the populations that stand to benefit from it. No group of persons, for example, men, women, pregnant women, children, and minorities, should be categorically excluded from the research without a good scientific or ethical reason to do so. Please provide the basis for concluding that the study population is representative of the population that stands to potentially benefit from this research.

All adult subjects who satisfy the inclusion/exclusion criteria are eligible for enrollment in this study regardless of sex, race or ethnicity.

When people who do not speak English are excluded from participation in the research, provide the scientific rationale for doing so. Individuals who do not speak English should not be denied participation in research simply because it is inconvenient to translate the consent form in different languages and to have an interpreter present.

Only participants who can read and speak English will be included in the current study, as the intervention and most assessment measures have not been validated for use in non-English speaking populations.

For guidance, refer to the following Mass General Brigham policy:

Obtaining and Documenting Informed Consent of Subjects who do not Speak English

<https://partnershealthcare.sharepoint.com/sites/phrmApply/aieipa/irb/Documents/Obtaining%20and%20Documenting%20Informed%20Consent%20of%20Non-English%20Speaking%20Subjects.pdf>

## RECRUITMENT PROCEDURES

Explain in detail the specific methodology that will be used to recruit subjects. Specifically address how, when, where and by whom subjects will be identified and approached about participation. Include any specific recruitment methods used to enhance recruitment of women and minorities.

Patients will be recruited via the MGH SCAD clinic through hospital flyers and cardiologist referrals. SCAD clinic cardiologists will obtain verbal permission from patients to share their information (e.g., name, phone number, MRN) with the study team. A member of the study team will then reach out to the patient to see if they are interested in participation. If the patient is not interested in study participation, study staff will discontinue contact. Patients will also be recruited through cardiologists' patient lists. The cardiologist and/or study staff will review the patient list for patients who have had SCAD in the past 3-18 months. Study staff will then send potentially eligible patients research invitation letters through Patient Gateway. Only patients who have agreed to be contacted about research studies will be sent a letter. We will use the required Research Invitation template (attached). Patients who proactively opt-out of the study will no longer be contacted. Patients recruited through hospital flyers may also contact the study team directly via phone or email, following the contact information on the flyer (e.g., study phone number and email address). The patient will be asked to provide the name of their cardiologist, who the study team will then contact to confirm the patient's history of SCAD, or the patient will be asked to give permission for study staff to review their electronic medical record to confirm a SCAD diagnosis.

Patients who are interested in study participation will be screened for eligibility over the phone by the study RA, who will be CITI certified and trained in all research procedures. The RA will explain the study procedures, answer any questions, and complete an eligibility screening, which will include: confirmation of the patient's age (> 18 years old), SCAD diagnosis in past 3-18 months, internet access, ability to speak and read English, no terminal illness, no severe mental illness or past-year psychiatric hospitalization, no cognitive impairments preventing informed consent, ability to complete research procedures, and availability for planned session times. Confirmation will be based on the patient's verbal report, study staff's clinical judgment, and/or the patient's medical history. The RA will consult with the PI and/or review the patient's electronic medical record to confirm any questions about eligibility. If participants meet study criteria, they will complete the informed consent process described below. The eligibility screener and phone scripts are included in the IRB submission.

Provide details of remuneration, when applicable. Even when subjects may derive medical benefit from participation, it is often the case that extra hospital visits, meals at the hospital,

parking fees or other inconveniences will result in additional out-of-pocket expenses related to study participation. Investigators may wish to consider providing reimbursement for such expenses when funding is available

Participants will be reimbursed using the Partners Advarra Participant Payments System. Advarra Payments is a cloud-based application that provides subjects with a reloadable Visa card that is credited with fixed stipends following specified data collection points. Participants will be informed of Advarra policy via the informed consent form. After agreeing to participate in the study, participants will also be asked to sign a “Advarra Participant Payment Card Acknowledgement of Receipt Form” form, to certify their understanding of Forte Payment policies. The form will require the subject to print and sign their name and provide their social security number. When mailing “Advarra Participant Payment Card Acknowledgement of Receipt Form” form is not an option (e.g., due to COVID work restrictions), participants will be asked to complete the form electronically via REDCap. Similar to the electronic consent process detailed below, study staff will email participants a link to an electronic version of the form. Participants will be given time to review Advarra guidelines, and when ready will review and electronically sign the “Advarra Participant Payment Card Acknowledgement of Receipt Form” form with study staff over the phone. Participants will then be provided with the option of receiving a mailed copy of the completed form through send secure email or through paper mail. All paper versions of the Advarra acknowledgement forms will be stored in a locked, study cabinet.

Participants will be remunerated up to \$50 via a reloadable debit card. Participants will receive \$10 each for completing 80% of actigraphy days, 80% of daily diaries, the baseline survey, the post-intervention survey, and the exit interview.

For guidance, refer to the following Mass General Brigham policies:

Recruitment of Research Subjects

<https://partnershealthcare.sharepoint.com/sites/phrmApply/aieipa/irb/Documents/Recruitment%20of%20Research%20Subjects.pdf>

Guidelines for Advertisements for Recruiting Subjects

<https://partnershealthcare.sharepoint.com/sites/phrmApply/aieipa/irb/Documents/Guidelines%20for%20Advertisements%20for%20Research%20Subjects.pdf>

Remuneration for Research Subjects

<https://partnershealthcare.sharepoint.com/sites/phrmApply/aieipa/irb/Documents/Remuneration%20for%20Research%20Subjects.pdf>

